**Assessment Schedule.** Participants will be assessed by an IE at baseline, 10-, 20- and 30-weeks post first treatment session. This study has a challenge of two treatments that possess substantially different number of sessions (e.g., 5 vs 8 to 15). The use of post-treatment assessment would be problematic given that participants in the two treatment conditions would be completing treatment at substantially different time from baseline assessment, with time to post-treatment being significantly greater in the PE condition than the WET condition. This is problematic as differences in outcome could be attributable to time since baseline assessment rather than treatment differences. Thus, in order to assure that time does not serve as a confound, assessments in this study will occur at equal intervals from baseline for both treatment conditions. Although we would expect that the majority of PE participants would complete treatment by the 10 week assessment period, it is well-documented that for CPT and PE the time to complete treatment varies substantially across participants, even when the treatment protocol is to attend twice weekly sessions (Gutner et al., 2016). In our prior study we requested participants attend twice weekly sessions for CPT but even with this system in place only 65% of the CPT participants completed treatment in 12 weeks and only one participant out of 63 completed treatment in 6 weeks (see Sloan, Marx, & Lee, 2018 for a discussion of this issue).

Participants in both treatment conditions will be considered a “treatment drop out” if they do not attend all treatment sessions. Consistent with the intent-to-treat approach, any participant who drops out will be asked to complete all assessments and all participants who are randomized will be included in data analyses for Study Aims 1 and 3. Treatment expectancy, credibility and satisfaction will be assessed to ensure that acceptability and feasibility of WET continues to be high with the veteran sample

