
## 9. Statistical Analysis Plan

Data will be analyzed in SPSS and MPlus software, which licenses are obtained by the Behavioral Science Division of the National Center for PTSD at VA Boston. The software is stored on a password protected server that is behind the VA firewall.

The equivalence of the treatment conditions will first be assessed according to key baseline variables (demographics and outcome variables) using t-tests, nonparametric equivalence, or Chi-square tests, depending on the type (continuous or dichotomous) and distribution (normal or

non-normal) of the data. Any variables that differ among groups will be used as covariates in the final analyses.

We anticipate some participant attrition during the trial. If a subject drops out of the study for any reason, we will vigorously pursue follow-up to minimize missing data. Yet, some data will inevitably be missing. Missing data will be handled in all analyses using direct maximum likelihood or multiple imputation techniques within MPlus 8.0 (Muthén & Muthén, 2018) under a missing at random (MAR) assumption. Modern missing data techniques such as direct ML increase statistical power and provide more accurate estimates of model parameters and standard errors, and are the recommended intent-to-treat approach for clinical trials (Enders, 2010). The primary analyses in this study will be performed on the intent-to-treat population that includes all patients randomized to a condition. Supplementary analyses will also be conducted examining outcomes in the subset of participants who complete a full course of treatment in each condition. In order to better understand the potential reproducibility of our findings, our conclusions from all analyses will be based on both the statistical significance of parameters and the magnitude of associated effect sizes.

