**Aim 1.** Our primary hypothesis that WET will be non-inferior to PE will be evaluated using similar analytic procedures conducted in our previous non-inferiority trial of WET (Sloan et al., 2018). Specifically, the non-inferiority margin of 10 will be used for comparing the two conditions on the primary PTSD outcome of CAPS-5 scores at the 10 week, 20 week, and 30 week assessments. The mean difference score between conditions will be calculated at each follow-up and the hypothesis of non-inferiority will be evaluated based on whether the entire 95% confidence interval of the mean difference is less than the margin of 10 points. We will then supplement this analysis by calculating additional effect sizes to characterize between condition differences in PTSD outcomes. Specifically, we will calculate Cohen's  $d$  (with 95% CI) for the mean difference in CAPS-5 scores at each time point and will calculate odds ratios (with 95% CI) for the proportion of participants who no longer meet diagnostic criteria for PTSD based on the CAPS-5 at each assessment period.

**Aim 2.** The comparison of treatment dropout in WET vs PE will be examined by calculating odds ratio effect sizes (with 95% confidence interval) for the proportion of participants who do not complete a full course of treatment (5 sessions) in WET and those who drop out of PE by session 5. The statistical significance of the between-group differences in dropout rates will then be evaluated using a chi-square difference test.

**Aim 3.** The exploratory analyses of moderators of WET and PE will be conducted using latent growth curve modeling conducted within Mplus. As the focus is not primarily on the nature of the growth trajectory, the intercept of the LGM will be centered on the baseline CAPS-5 assessment (i.e., first slope loading fixed to 0), the slope loading for the final time point will be fixed at 1.0, and loadings for all intermediate assessments will be freely estimated. The mean and variance of the slope factor in this model will reflect the total change in and individual differences in change

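### The primary CAPS-5 analysis names a contrast but no model, and nothing requires baseline or the other visits to enter it, so its missing-data handling and precision are left open

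*Combined protocol and SAP*

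**What the plan says.** Section 9 (Statistical Analysis Plan), Aim 1, states the contrast: "The mean difference score between conditions will be calculated at each follow-up". Non-inferiority is judged on whether "the entire 95% confidence interval of the mean difference is less than the margin of 10 points". The only pointer to a method is that the hypothesis "will be evaluated using similar analytic procedures conducted in our previous non-inferiority trial of WET"; those procedures are not reproduced.

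The opening paragraphs of section 9 add three general rules:
- "Missing data will be handled in all analyses using direct maximum likelihood or multiple imputation techniques within MPlus 8.0", "under a missing at random (MAR) assumption".
- The primary analyses are by intention to treat. The Assessment Schedule text in section 7 likewise says that "all participants who are randomized will be included in data analyses for Study Aims 1 and 3".
- Baseline variables become covariates if the arms are found to differ on them. Baseline CAPS-5 therefore enters Aim 1 only if it happens to be unbalanced.

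Longitudinal models are specified elsewhere. The exploratory moderator analyses of Aim 3 "will be conducted using latent growth curve modeling conducted within Mplus", with the slope loadings described. The WHOQOL-BREF in Aim 4 gets a hierarchical linear model with stated covariance structures. The primary analysis is the least specified of the three.

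**The concern.** Direct ML recovers information about a missed week-20 score only through other variables in the same likelihood. With week-20 CAPS-5 as the outcome and arm as the only predictor, a participant without that score contributes nothing, and the estimate is the difference in observed means. The commitments to all randomized participants and to MAR would then not be met in substance for the primary result.

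Imputation from the other visits, which the same sentence permits, can give a different answer from the same data. Two analysts could follow the text faithfully and report different intervals against the margin. The error could go either way. If improved PE participants stop attending assessments, the observed difference shifts toward non-inferiority; if unimproved ones do, it shifts away.

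A second loss remains even when missing scores are handled well. An unadjusted visit difference leaves out baseline CAPS-5, which is collected before randomization.

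**Working it through.** **Inputs from the documents.** 90 per arm, 1:1 allocation; CAPS-5 at baseline and weeks 10, 20 and 30; margin 10; 95% interval. The plan states no SD, power, visit correlation or missed-assessment rate, so there is no figure on this point to reproduce.

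**Assumptions.** SD 13; correlation 0.4 with baseline and r = 0.6 to 0.8 between weeks 10 and 20; week 20 missing in 30% of PE and 10% of WET; log-odds of missing b = 0.8 per SD of week-10 score; true difference 0.

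**Step 1: bias of the single-visit, arm-only fit.** Let z be the standardized week-10 score and p(z) the logistic probability of missing week 20. Among those observed, the mean of z moves in size by

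b × E[p(1 − p)] / (1 − rate).

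- PE, 30% missing: E[p(1 − p)] = 0.187, so 0.8 × 0.187 / 0.7 = 0.213.
- WET, 10% missing, same dependence: E[p(1 − p)] = 0.085, so 0.8 × 0.085 / 0.9 = 0.075.

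The week-20 observed mean moves by r × SD times that shift.

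| Scenario | r = 0.6 | r = 0.8 |
|---|---|---|
| Loss depends on score in PE only | 0.6 × 13 × 0.213 = 1.7 | 0.8 × 13 × 0.213 = 2.2 |
| Same dependence in both arms, unequal rates | 0.6 × 13 × (0.213 − 0.075) = 1.1 | 0.8 × 13 × (0.213 − 0.075) = 1.4 |
| Same dependence and same rate | 0 | 0 |
| MCAR (b = 0) | 0 | 0 |

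Simulation at 90 per arm gives 1.1 to 2.3 points for the first two rows. A joint model stays at about 0.1 or less.

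**Step 2: what that does to the decision.** Observed numbers are 90 × 0.7 = 63 and 90 × 0.9 = 81, so SE = 13 × √(1/63 + 1/81) = 2.18. Suppose the true difference is exactly 10 and the better PE participants are lost. The false non-inferiority rate is Φ(−1.96 + 1.7/2.18) = 12% at r = 0.6 and Φ(−1.96 + 2.2/2.18) = 17% at r = 0.8, against a nominal 2.5%.

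**Step 3: separate check at week 30.** Four visits simulated, SD 13, correlation 0.5 to 0.7, dropout depending on the last observed score, large samples for bias:

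| Loss pattern | Observed-case bias |
|---|---|
| Equal rate and mechanism | about 0 |
| PE loses more high scorers (40% v 13-14%) | +1.3 to +1.9 (against WET) |
| Arms lose opposite kinds of participant | −2.6 to −3.8 (favouring WET) |

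Across these patterns, joint ML of all visits had bias −0.03 to +0.13. Imputation from all visits followed by the same per-visit difference had 0.00 to +0.16. Adjusting a single visit for baseline alone left −0.8 to +0.5. At 90 per arm, correlation 0.6 and a true difference of 10, false non-inferiority rates in the three rows were 0.024, 0.003 and 0.286 for observed cases, against 0.025, 0.026 and 0.021 for joint ML.

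**Step 4: precision under the favourable reading.** Using all visits but not baseline adjustment, the gain still available with complete data is 1 − √(1 − 0.4²) = 8.3% of the sampling SD. With some visits missing, simulation puts it at about 6-8%. Relative to the observed-case difference, the joint model's sampling SD is about 7-15% smaller.

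**The case against.** The strongest reply is that the Aim 1 sentence names a contrast, not an estimator. A mean difference at each follow-up is also what a joint model reports. The missing-data rule covers all analyses, and an arm-only single-visit fit would make it empty. Reading the passages together, it is at least as natural to suppose that missing scores are recovered first and the visit difference taken afterwards. The cited earlier trial may also define the model. This stands. A reader might infer that the plan rejects a joint model, or that its ML handling recovers nothing; the documents say neither, and they expressly permit multiple imputation, which works when it uses all visits.

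A reader might also infer from Hypothesis 2a, or from the background rates (about 36% for first-line therapies, 5-10% for WET), that CAPS-5 visits will be missed unequally. Those concern treatment dropout. Participants who drop out are still asked to complete every assessment, follow-up is to be pursued vigorously, and telephone assessment is available. Loss related to symptoms is possible: section 10 provides for withdrawal after sustained worsening, and the adverse-event text continues assessments only with the participant's agreement. But its rate and its difference between arms are unknown.

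Finally, a bias of about 2 points is modest beside a margin of 10. If the true difference is 0 and the bias is an adverse 2.2, non-inferiority is still concluded about 95% of the time: Φ((10 − 2.2)/2.18 − 1.96). The harm is mainly to error control when the truth lies near the margin.

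None of this supplies the missing specification: the choice between ML and imputation, and the variables that enter, remain open for the primary result.

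**Conclusion.** The point holds in conditional form. The plan fixes the primary contrast but not the model, does not choose between direct ML and imputation, and does not require baseline or other-visit CAPS-5 to enter.

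- If each visit is fitted alone with arm as predictor, the result is an observed-case comparison. It is biased under MAR when loss depends on earlier scores and differs in rate or direction between arms: about 1 to 2.3 points at SD 13 with 30% v 10% missing. Opposite directions of loss give more, but nothing in the documents suggests that pattern. Under MCAR or equal mechanisms there is no bias.
- If imputation with all visits is used, that bias goes, and what remains is about 6-8% of sampling SD that baseline CAPS-5 could remove at an assumed correlation of 0.4.

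The SD, correlations, missing rates and mechanisms are all assumptions, so the sizes are illustrative. The per-visit contrast itself is not a defect. The change is worth making because one named model improves the result under either reading, using data already collected.

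**What to change.** In section 9, Aim 1, replace the sentence on the mean difference with wording such as: *The WET minus PE differences in CAPS-5 at weeks 10, 20 and 30, with 95% CIs, will be estimated from one direct-ML model in Mplus containing CAPS-5 at baseline and weeks 10, 20 and 30 for all randomized participants, with a common baseline mean, free arm-by-visit means after baseline and an unstructured covariance. This is the primary analysis.*

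If multiple imputation is kept as a check, require arm and all four CAPS-5 visits in the imputation model and baseline CAPS-5 in the analysis model.

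The cost is SAP wording and a few lines of code in software the plan already names. No extra data, staff or participants are needed. The change should be dated before outcomes are examined by arm.

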## 2. Aims/Objectives

The proposed study will examine the extent to which WET is non-inferior in reducing PTSD symptom severity among veterans with PTSD relative to the widely used but more time intensive, PE.

We propose the following aims and hypotheses:

**Aim 1:** Determine if WET is non-inferior relative to PE in terms of PTSD symptom severity.

**Hypothesis 1a.** WET will be non-inferior to PE at both 10- and 20-weeks after initiating treatment. PTSD symptom severity will be assessed using the Clinician Administered PTSD Scale for DSM-5.

**Hypothesis 1b.** Non-inferiority will be maintained 30 weeks after initiating treatment.

**Aim 2.** Determine if WET has better treatment retention than PE.

**Hypothesis 2a.** WET will have significant fewer treatment dropouts compared with the first 5 sessions of PE.

**Aim 3:** We will explore potential moderators of treatment effects for both WET and PE. Given that prior studies of PTSD treatment moderators have shown mixed results, this aim is exploratory. Our exploratory analyses will include variables that have been tested in other studies (e.g., age, sex, combat era, pre-treatment depression, social support, and estimated IQ).

**Aim 4:** Functioning will be examined as a secondary outcome.

Hypothesis: We expect that participants assigned to both PE and WET will display significant improvements in functioning as measures by the WHOQOL-BREF, however, we do not expect to find between condition differences.

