experience of that event on a 6-point nominal scale. There are no published data on the psychometric properties of the LEC-5, but is nearly identical to the original LEC, which has high internal consistency and test-retest reliability (Weathers et al., 2013). The worst traumatic event identified at the initial assessment is recorded and used for all subsequent administrations of the CAPS-5. The LEC-5 requires approximately 15 minutes to complete.

The **World Health Organization Quality of Life BREF** (WHOQOL-BREF; WHO, 1998) instrument comprises 26 items, which measure the following broad domains: physical health, psychological health, social relationships, and environment. The WHOQOL-BREF is a shorter version of the original instrument that is more convenient for use in large research studies or clinical trials. This measure requires 5-10 minutes to complete. It is included in this study to examine quality of life improvement as a secondary outcome measure.

The **Personality Inventory for DSM-5 – Brief Form** (PID-5-BF; American Psychological Association, 2013) is a 25-item self-report measure that assesses five personality trait domains associated with personality dysfunction: negative affect, detachment, antagonism, disinhibition, and psychotism. The PID-5-BF will be administered at each assessment occasion to measure changes in maladaptive personality dimensions as a result of treatment.

**Multidimensional Scale of Perceived Social Support** (MSPPS; Zimet, Dahlem, Zimet & Farley, 1988) is a 12 item self-report measure of social support. Social support has been found to moderate outcome following a traumatic event. This measure will be included at baseline assessment to examine if social support moderates treatment outcome. In addition, the MSPPS will be administered at each assessment occasion to measure changes in perceived social support during treatment.

**Test of Premorbid Functioning** (TOPF) is a premorbid estimate of intelligence that takes 5-10 minutes to administer and requires participants to read a list of up to 70 words. This measure will be administered at baseline. In our prior non-inferiority study we found estimated IQ served as a moderator for CPT treatment outcome (with higher IQ predicting better outcome) but estimated IQ did not serve as a moderator for WET (Marx et al., 2017).

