in PTSD symptoms across the full assessment period. The hypothesized moderators (age, sex, combat era, social support, time since index trauma event, and estimated IQ) will then be specified as predictors of the slope factor in separate models. These LGM will be conducted for the full sample first, and will then be conducted separately within each treatment condition to examine whether moderators of treatment outcome are consistent across WET and PE. To aid in the interpretation of clinical significance, results from LGM analyses will be converted to effect size metrics within 95% confidence intervals following established procedures (Feingold, 2015). Evaluation of model fit in the LGM models will be examined using fit diagnostics (i.e., standardized residuals) and common fit statistics (i.e., root mean square error of approximation) following the associated cutoff criteria recommended by Hu & Bentler (1999).

We will conduct additional exploratory analyses to evaluate characteristics of patients who require additional WET sessions, as well as characteristics of patients who require more than 12 PE sessions. These analyses will be conducted using logistic regression with dependent variable being more than 12 sessions of PE or more than 5 sessions of WET (conducted separately for each treatment condition). We will include characteristics such as age, time since trauma event, combat era, baseline PTSD symptom severity, baseline depression, baseline social support, baseline estimated IQ.

**Aim 4:** Follow standard practice for examining secondary outcome measures in a non-inferiority trial (e.g., Thompson-Hollands et al., 2018), we will use hierarchical linear modeling (HLM; Raudenbush & Bryk, 2002) to determine impact of treatment on functional impairment as measured by the WHOQOL-BREF. Analyses will be conducted using an autoregressive covariance matrix at level 1 (within person) and a scaled identity matrix at level 2 (between persons). A between-treatments variable will be included in the analysis, as functional impairment is a secondary outcome and therefore not subject to the same noninferiority analyses. Guidelines from Cohen (1988) will be used to interpret the within- and between-condition effect sizes ( $d$ ).

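### Exploratory Aim 3 asks whether moderators act alike in WET and PE, but plans no estimate, interval or test of the between-arm difference

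*Combined protocol and SAP*

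**What the plan says.** Section 2 labels Aim 3 exploratory and attaches no hypothesis to it. Section 9, Aim 3, sets out a latent growth model of CAPS-5 with the slope loading fixed at 0 at baseline and 1.0 at the last assessment; "loadings for all intermediate assessments will be freely estimated". Six variables are named: "The hypothesized moderators (age, sex, combat era, social support, time since index trauma event, and estimated IQ"). Each is entered in its own model as a predictor of the slope factor.

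The models are fitted first in the full sample and "will then be conducted separately within each treatment condition to examine whether moderators of treatment outcome are consistent across WET and PE". For reporting, "results from LGM analyses will be converted to effect size metrics within 95% confidence intervals". The general rule for drawing conclusions, earlier in section 9, is that "our conclusions from all analyses will be based on both the statistical significance of parameters and the magnitude of associated effect sizes".

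Neither section 9 nor the remarks on moderators in sections 2 and 8 name a treatment-by-moderator term, a two-group model with an equality test, or an interval for the WET-PE difference in the moderator path.

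**The concern.** The full-sample model shows who improves more overall, so it identifies predictors of change. Each within-arm model shows who improves more under that treatment. Neither estimates whether the relation differs between treatments, which is what the last step sets out to learn. The planned confidence intervals belong to each model's own results, not to the contrast between arms.

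Without a planned contrast, the natural shortcut is to look at which arm's path is significant. The main risk is then false discordance: a variable with the same effect in both arms is reported as mattering for one treatment only. Section 8 (Test of Premorbid Functioning) describes a result from the previous trial in that form: estimated IQ moderated outcome for the comparator therapy, "but estimated IQ did not serve as a moderator for WET". The documents do not say how that contrast was tested, so it shows only the kind of statement Aim 3 could produce.

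**Working it through.** The documents give no power, alpha or effect size for Aim 3, so there is no planned figure to reproduce.

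**Inputs from the documents.** 90 per arm (section 6), 1:1 allocation, six moderators, slope scaled identically in each model.

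**Assumptions.** Each moderator-slope path is treated as a correlation r with an observed slope; two-sided alpha is 0.05, to match the 95% intervals; true r runs from 0 to 0.4. The discordance rule (only one arm significant) is also assumed.

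**Within-arm power.** On the Fisher z scale SE = 1/√(n − 3) = 1/√87 = 0.107. A path is significant when |r| exceeds tanh(1.96/√87) = 0.207. With p the power in one arm, two independent arms with the same true r disagree with probability 2p(1 − p):

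| True r in both arms | p (n = 90) | 2p(1 − p), n = 90 | 2p(1 − p), n = 72 |
|---|---|---|---|
| 0 | 0.050 | 9.5% | 9.5% |
| 0.1 | 0.155 | 26% | 23% |
| 0.2 | 0.473 | 50% | 48% |
| 0.3 | 0.823 | 29% | 39% |
| 0.4 | 0.977 | 4.5% | 11% |

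The n = 72 column assumes 20% of each arm contributes nothing. A direct test, z = (atanh r₁ − atanh r₂)/√(2/(n − 3)), disagrees about 5% of the time in every row; simulation confirmed this. For six independent moderators with no effect, the chance of at least one false discordance is 1 − (1 − 0.095)⁶ = 45% under the informal rule, against 1 − 0.95⁶ = 26.5% with direct tests.

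**Adding a size condition.** By simulation at n = 90, also requiring the two correlations to differ by at least 0.2 (an invented threshold) lowers r = 0.1, 0.2 and 0.3 to 11%, 15% and 11%.

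**Other forms of the model.**
- With the slope kept latent in a two-arm growth model (assumed slope SD 12, residual SD 6 or 9), discordance was 50% or 48% at r = 0.2 and 35% or 41% at r = 0.3. A Wald test of equal paths gave 4.5% to 5.7%.
- For a binary moderator present in an assumed 20% of each arm, with the same d in both arms, discordance was 32%, 50% and 25% at d = 0.3, 0.5 and 0.8, against about 5% for the direct test.

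**Detecting a real difference (n = 90).** Here the informal rule counts one arm significant, or both with opposite signs:

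| True r in the two arms | Informal rule | Direct test |
|---|---|---|
| 0 and 0.3 | 81% | 53% |
| 0 and 0.4 | 95% | 80% |
| −0.15 and +0.15 | 50% | 51% |
| 0.3 and 0.6 | 18% | 72% |

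The informal rule is therefore not uniformly worse at detection. Its higher rates in the first two rows come with the false discordance shown above.

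**Example.** Estimates of 0.22 (95% CI 0.01 to 0.41) in one arm and 0.19 (−0.02 to 0.38) in the other read as moderation in one arm only. The difference in Fisher z is 0.224 − 0.192 = 0.03, with half-width 1.96 × √(2/87) = 0.297, so the interval is −0.27 to 0.33.

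**The case against.** The strongest reply is that these error rates belong to a rule nobody has written. The plan bases conclusions on effect size as well as significance, and provides intervals. With a stricter size condition the problem shrinks further: requiring a gap of at least 0.25 in r gives 4.6% to 8.0% for r = 0 to 0.3 and 2.0% at r = 0.4, and a gap of at least 0.3 gives 1.1% to 3.7%, below the direct test. The 50% is also the mathematical maximum of 2p(1 − p), which r = 0.2 happens to reach at this sample size. The n = 72 case is pessimistic, because dropouts are asked to complete assessments and maximum likelihood or multiple imputation is planned.

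Further, the separate models already contain what is needed. The arms are independent and the slope is scaled alike, so the difference and its standard error, √(SE²_WET + SE²_PE), follow from the two unstandardised paths. The direct test has modest power, and the aim is exploratory.

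Most of this stands as a limit on size: the rates are conditional illustrations. It does not remove the gap. That the result can run from much worse than a direct test to better than it, depending on an unstated criterion, is a reason to fix the criterion in advance. That the difference can be derived cheaply is a reason to plan it. Readers given only effect sizes standardised within arm could not recover it reliably if SDs differ between arms.

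**Conclusion.** The concern holds, as a minor point. Aim 3 poses a between-arm question and plans only pooled and within-arm answers. How much harm follows depends on how consistency is judged, which the plan leaves open. Under the significance-only reading, false discordance at 90 per arm ranges from 4.5% to 50% over r = 0 to 0.4, and a size condition reduces it, possibly to below 5%. The correlations, SDs, missing fraction and alpha are all assumptions. No confirmatory conclusion rests on this aim, and the primary non-inferiority comparison is untouched.

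**What to change.** Replace the separate-arm step in section 9, Aim 3, with wording such as:

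> For each baseline moderator, a two-group growth model (WET, PE) will be fitted to all randomised participants, with intermediate loadings, factor variances and residual variances free in each arm. The between-arm difference in the unstandardised moderator-slope path will be reported with its 95% CI and a Wald test of equal paths. Within-arm paths are descriptive, and full-sample main effects will be called predictors. These tests are exploratory and unadjusted, and the number run will be reported. A non-significant difference does not establish consistency; the interval will be interpreted.

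A single model with condition, moderator and their product as predictors of the slope is an alternative. The two-group form keeps arm-specific loadings, as the planned separate models do, which suits treatments of different length.

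The cost is SAP wording plus a grouping statement and one contrast per Mplus model; no new data are needed. The drawback is imprecision: about ±0.30 in Fisher z, or ±3.7 to 4.1 CAPS-5 points of change per SD of moderator in the simulated growth model. Power for r = 0 against 0.3 is 53% with an observed slope and 38% to 44% with a latent one. Six independent unadjusted tests carry a 26.5% chance of at least one false positive. The wide intervals show readers how little this trial can say about differential moderation.
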